1.0 INTRODUCTION

Anatomical changes and physiological processes taking over tooth extraction were studied in the past (Cryer 1916, Rogers and Applebaum 1941, Pietrokovski and Massler 1967), however since the introduction of dental implants in modern odontology these issues and the prevention of edentulous jaw atrophy have become an important topic. The survival of implants and their ability to provide adequate function and esthetics are strictly correlated with their proper positioning in relation to the alveolar housing, the neighboring teeth and the occluding dentition. It is thus easily understood the tremendous effort that has been used by many researchers and practitioners in reducing this unavoidable modeling and remodeling process.

1.2 ALVEOLAR RIDGE REMODELING

Maxillary and mandibular bony complexes are composed by several anatomical structures with a proper function, composition and physiology: i) basal bone that develops together with the overall skeleton, and forms the body of mandible and maxilla; ii) alveolar process that develops following tooth eruption and contains the tooth alveolus; iii) the bundle bone that lines the alveolar socket, extends coronally forming the crest of the buccal bone, and makes part of the periodontal structure as it encloses the external terminations of periodontal fibres (Sharpey's fibers).

After tooth extraction, bundle bone appears to be the first bone to be absorbed (Boyne 1966, Hsieh, Devlin et al. 1994, Devlin and Sloan 2002) whereas alveolar bone is gradually absorbed throughout life (Carlsson and Persson 1967, Ashman 2000). The remodeling process results in a ridge morphology reduced in vertical height and more palatal in relation to the original tooth position (Cryer 1916, Rogers and Applebaum 1941, Pietrokovski and Massler 1967, Pietrokovski and Massler 1967).

Studies from the Lindhe's group suggest bone resorption to occur in 2 phases (See Figure 1). During the first phase, bundle bone is rapidly resorbed and replaced with woven bone leading to a great reduction in bone height especially in the buccal aspect of the socket, as its crestal portion is comprised solely of bundle bone (Araujo and Lindhe 2005). In-vitro animal studies have demonstrated the osteogenic potential of PDL derived cells (Cho, Matsuda et al. 1992, Ramakrishnan, Lin et al. 1995) although the role of bundle bone in providing cells for the regeneration of new bone has been more recently challenged (Steiner, Francis et al. 2008) as new bone formation appears to initiate from the surrounding alveolar bone cells (Boyne 1966, Hsieh, Devlin et al. 1994, Devlin and Sloan 2002). Lindhe's group reported that the presence or absence of PDL in the extraction

socket does not influence the features of healing after 3 months (Cardaropoli, Araujo et al. 2005). During the second phase, the outer surface of the alveolar bone is remodeled causing an overall horizontal and vertical tissue contraction. The reason for this remodeling process is still not well understood. Disuse atrophy, decreased blood supply, and localized inflammation might play important roles in bone resorption. However, it is now apparent that bone remodeling is a complex process involving structural, functional, and physiologic factors and that surgical trauma from extraction induces microtrauma to surrounding bone, which accelerates bone remodeling (Garetto, Chen et al. 1995).

Resorption rate of the alveolar ridges is faster during the first six months following the extraction (Pietrokovski and Massler 1967, Johnson 1969) and proceeds at an average of 0.5-1.0% per year for the entire life (Carlsson and Persson 1967, Ashman 2000). The height of a healed socket never reaches the coronal level of bone attached to the extracted tooth and horizontal resorption seems to be greater in the molar region compared to the premolar area (Schropp, Kostopoulos et al. 2003, Hammerle, Araujo et al. 2012). Schropp *et al.* estimated two-thirds of the hard and soft tissue changes occur in the first 3 months. The authors reported 50% of crestal width to be lost in a 12-month period (corresponding to 6.1 mm; range 2.7 to 12.2 mm) 2/3 of which (3.8mm; 30%) occurred in the first 12 weeks. When examining the premolar area only a loss of alveolar ridge width of 4.9mm (45%) was reported, of which 3.1mm (28.4%) occurred in the first 12 weeks (Schropp, Wenzel et al. 2003). A recently published systematic review (Tan, Wong et al. 2012) reported a greater horizontal alveolar ridge reduction (29-63%; 3.79 mm) than vertical bone loss (11-22%; 1.24 mm on the buccal, 0.84 mm on mesial and 0.80 on distal sites) at 6 months. In a long-term study, Ashman reported alveolar bone shrinkage of 40-60% in height and width within the first 2-3 years (Ashman 2000, Ashman 2000).

1.3 SOCKET HEALING

Immediately after tooth extraction, the alveolar socket is filled by blood clot that is replaced by granulation tissue within 1 week (see Figure 1) (Amler 1969). In the healing of a skin wound, epithelial cells migrate underneath and are protected by the blood clot. In socket healing instead, the epithelium migrates over the granulation tissue to cover the healing socket (Mangos 1941). This happens because this inflammatory tissue is recognized as a connective tissue by the epithelial cells therefore cellular migration occurs over its surface. This is important when we examine Guided Bone Regeneration applied to socket grafting. Starting from the apical and lateral residual bony walls the granulation tissue is rapidly remodeled to provisional matrix. Mineralizing processes occur leading to the formation of woven bone that eventually is replaced by mature lamellar bone (Trombelli, Farina et al. 2008).

Early human histological investigations reported that extraction sockets are filled with delicate cancellous bone in their apical two thirds at 10 weeks, and are completely filled with bone at 15 weeks (Mangos 1941). Increased radiopacity is demonstrated as soon as 38 days and radiopacity similar to that of the surrounding bone at 105 days (Mangos 1941). These figures might be partially biased as specimens were harvested from cadavers therefore their late age and their systemic condition might have led to delayed wound healing capabilities. On the other side, animal studies demonstrate accelerated healing as 3 weeks old extraction sockets in humans compare with to 9-10 days old sockets in dogs and a 3½ months sockets in humans compares with 8 weeks sockets in dogs (Clafin 1936).

1.4 RATIONALE FOR EXTRACTION SOCKET PRESERVATION

Bone formation in the alveolar socket is a naturally occurring event as long as surrounding alveolar walls remain intact; however the alveolar ridge volumetric contraction may impair proper implant placement. To reduce loss of alveolar bone to acceptable levels, several surgical techniques have been proposed. Reducing the extraction trauma and limiting flap elevation (Fickl, Zuhr et al. 2008) are essential for obtaining success in each of these procedures. Animal studies show mixed results when evaluating differences in ridge remodeling between flapped and non-flapped extraction sockets (Blanco, Nunez et al. 2008, Fickl, Zuhr et al. 2008, Fickl, Zuhr et al. 2008, Araujo and Lindhe 2009, Vignoletti, Matesanz et al. 2012) although it has been hypothesized that by disrupting the thin layer of cells that comprises the osteogenic layer of the adult periosteum, the elevation of a flap might diminish the ability of periosteal cells to regenerate bone while an undisturbed periosteum maintains its osteogenic potential (Melcher 1969, Melcher 1971, Melcher 1976, Araujo and Lindhe 2005). It is possible that flap elevation affects alveolar dimensional alterations only in the short-term (Tan, Wong et al. 2012). In guided bone regeneration 4 methods can be used to increase the rate of bone formation and to augment bone volume: osteoinduction by the use of appropriate growth factors; osteoconduction, where a grafting material serves as a scaffold for new bone growth; distraction osteogenesis, by which a fracture is surgically induced and bone fragments are then slowly pulled apart; and finally, guided tissue regeneration, which allows spaces maintained by barrier membranes to be filled with new bone (Hammerle and Karring 1998). Utilizing these concepts it has been proposed guided bone regeneration with non-resorbable and absorbable membranes, several types of bone grafts with or without use of barrier membranes or the addition of mucogingival treatments and more recently the use of bioactive molecules for the generation of bone in the extraction socket. When analyzing the results of the following described studies it should be kept in mind the goal of the additional service that is provided to the patient, which include:

- To enable installation and stability of a dental implant
- To reduce loss of alveolar bone volume
- To reduce need for additional bone grafting procedures
- To enable the generated tissues to provide implant osseointegration
- To improve the esthetic outcome of the final prosthesis
- To regenerate bone faster allowing earlier implantation and restoration

1.4.1 RIDGE PRESERVATION WITH BONE GRAFT

The clinical advantages of bone fillers in alveolar ridge volume preservation and prevention of additional bone grafting procedure are largely supported by the available literature (Sclar 1999, Iasella, Greenwell et al. 2003, Luczyszyn, Papalexou et al. 2005, Fickl, Zuhre et al. 2008). Minimal ridge remodeling has been observed when using non-resorbable hydroxyapatite crystals covered by a rotated pediculated split thickness palatal flap (Nemcovsky and Serfaty 1996), DFDBA covered with an ePTFE membrane (Brugnami, Then et al. 1996) or even allogenic or xenogenic bone grafts covered with nothing but a collagen plug (Sclar 1999, Wang and Tsao 2007) (Figure 1). Histological evidence demonstrates that bone formation occurs over the surface of the implanted osteoconductive graft particles (Artzi, Tal et al. 2000, Artzi, Tal et al. 2001). At 3 months or later grafted sockets generally demonstrate higher mineralized tissue figures, when considering both new vital bone and remaining graft particles, but the formation of new bone appears to be similar in grafted and non-grafted sites. It can be extrapolated that residual particles occupy part of the volume that would have been occupied by bone marrow if bone grafting were not adopted (Araujo, Linder et al. 2008).

[figure not shown]

Fig 1

Figure 1. Healing of the extraction socket with and without socket grafting. When socket grafting is not adopted major alveolar ridge resorption occurs. In a first phase, initially the blood clot, subsequently the granulation tissue and later the provisional matrix and the woven bone fill up the alveolus. The bundle bone is completely resorbed causing a reduction in the vertical ridge. In a second phase the buccal wall and the woven bone are remodeled causing the horizontal and further vertical ridge reduction. When socket grafting is adopted, the first phase and vertical bone reduction still occur, however the second phase and the horizontal contraction are reduced.

At earlier healing stages (2 weeks) instead, grafted sockets demonstrate xenograft particles enclosed in connective tissue and coated by multinucleated cells when nongrafted sites already show newly formed woven bone occupying most of the socket (Araujo, Linder et al. 2009). This response is typical of a foreign body reaction which can be elicited by the xenograft and though it is clinically non-immunogenic, non-toxic and chemically inert (Luttikhuisen, Harmsen et al. 2006), it results in a delayed healing response during the earliest stages of socket healing. Many articles reported only a partial resorption of the grafted particles at short and long timepoints (Brugnami, Then et al. 1996, Becker, Clokie et al. 1998, Iasella, Greenwell et al. 2003, Wang and Tsao 2008, Araujo, Linder et al. 2009, Mordenfeld, Hallman et al. 2010, Rasperini, Canullo et al. 2010) arising doubts on the achievement of the osteointegration of implants inserted in augmented sites and on the success of the restorative therapy. Histological animal studies (Fiorellini, Kim et al. 2007, De Santis, Botticelli et al. 2011) evaluated the osteointegration of dental implants following bone regeneration performed with different bone fillers and observed a bone-to-implant contact similar to that of implants placed in pristine bone (40% to 65%). Furthermore clinical studies observed that good primary stability can be reached at implant insertion, that the grafting procedure does not impair early osteointegration (Carmagnola, Adriaens et al. 2003, Molly, Vandromme et al. 2008) and that implants placed in bone regenerated using mineralized grafts are able to sustain loading and provide similar long-term results as those placed in pristine bone (Fiorellini and Nevins 2003).

Mineralized grafting materials may interfere with the earliest stages of socket healing and their elimination may require several years (Araujo, Linder et al. 2008) or they may in fact be nonresorbable even in the long term (Mordenfeld, Hallman et al. 2010). On the other side, their ability to prevent crestal ridge resorption and sustain long-term implant success has been clearly demonstrated (Carmagnola, Adriaens et al. 2003, Fiorellini and Nevins 2003, Molly, Vandromme et al. 2008).

Other advantages in the use of osteoconductive grafting material were reported by a clinical and histological human study of post-extractive defects in posterior maxillary area treated with a xenogenic graft. In this study, Rasperini *et al.* confirmed the space maintaining activity of the implanted material and reported a decreased demand for sinus lift augmentation procedure when the socket preservation procedure was performed (Rasperini, Canullo et al. 2010). Through a computed tomography analysis of maxillary anterior post extractive defects, Nevins *et al.* reported that 79% of grafted sites underwent less than 20% buccal plate loss, while 71% of nongrafted sites demonstrated more than 20% buccal plate loss. An interesting finding of this investigation was that even the experienced surgeons participating to this study were not able to predict the fate of the

buccal plate, therefore the authors suggested socket grafting to be performed at the time of extraction (Nevins, Camelo et al. 2006).

1.4.2 FREE SOFT-TISSUE GRAFT OVER MINERALIZED BONE GRAFT

The placement of free soft-tissue graft to cover the augmented alveolar socket was introduced to minimize the soft tissue shrinkage, optimize aesthetical results of implant restoration and obtain a primary closure that may preserve the graft from bacterial infections and secondary graft failure (Stimmelmayer, Allen et al. 2010, Thalmeier, Hinze et al. 2010). The first attempt to cover the socket graft with an autogenous soft tissue implant was described by Landsberg and Bichacho in 1994 (Landsberg and Bichacho 1994). Nevins *et al.* suggested the use of soft tissue grafts to improve ridge topography after tooth extraction (Nevins and Mellonig 1994) and in combination with immediate implant placement (Landsberg 1997).

In 1999 Tal described the survival of circular connective tissue grafts placed over extraction sockets treated either with DFDBA or Bio-Oss. They found that the survival was not dependent on the adopted graft and that at 1 week 18/42 grafts were vital, 13/42 were partially vital and 11/42 were non-vital. Complete closure of all sockets occurred 4 weeks post extraction. The Authors noted that more often partially vital grafts maintained their vitality over the socket area more than on the graft margins; they concluded that the nourishment could be originated from plasmatic elements in the socket blood clot more than from vessels originating from the periphery of the graft (Tal 1999).

1.4.3 GEISTLICH MUCOGRAFT® SEAL OVER MINERALIZED BONE GRAFT

The use of Geistlich Mucograft® is an alternative to autogenous soft tissue graft. The 3-D collagen matrix can be used for root coverage procedures and/or for gain of keratinized tissue (Nevins, Nevins et al. 2011, Lorenzo, Garcia et al. 2012). Geistlich Mucograft® Seal can be used over mineralized bone graft (BioOss® Collagen) after minimally invasive tooth extraction in order to preserve hard and soft tissue volume for future implant placement (Jung, Philipp et al. 2013). The collagen of Geistlich Mucograft® is processed to favor immediate blood clot stabilization. This leads to early vascularization (Ghanaati, Schlee et al. 2011, Rocchietta, Schupbach et al. 2012), facilitates soft tissue cell ingrowth (Ghanaati, Schlee et al. 2011), and excellent integration of the 3-D matrix within the surrounding tissues (Ghanaati, Schlee et al. 2011, Rocchietta, Schupbach et al. 2012). In a clinical trial, Thoma and collaborators evaluated whether Geistlich Mucograft® Seal could improve early wound healing and esthetics, and decrease wound sensitivity compared to spontaneous healing (Thoma, Sancho-Puchades et al. 2012). The authors reported that the defect area

decreased over time for both treatments and re-epithelization was completed in all subjects by day 15. The defect area was significantly smaller for the Geistlich Mucograft® Seal (mean \pm SD: 19.3 \pm 3.4 mm²) compared with control (21.3 \pm 3.3 mm²) at day 4 ($p < 0.05$), and at day 8 (Geistlich Mucograft® Seal: 11.7 \pm 2.5 mm²; control: 13.6 \pm 2.9 mm²; $p < 0.01$). The color match was more favorable for Geistlich Mucograft® Seal at day 4, 8 and 29 ($p > 0.05$). Somatosensory measurements revealed slightly lower wound sensitivity at day 4 for Geistlich Mucograft® Seal compared with control. Jung and investigators compared the use of Geistlich Mucograft® Seal along with BioOss® Collagen to 3 different socket preservation approaches; 1. BioOss® Collagen along with free gingival graft, 2. β -tricalcium-phosphate-particles with polylactid coating (β -TCP), and 3. Spontaneous healing (control). Results demonstrated that the application of BioOss® Collagen, covered with Geistlich Mucograft® Seal or Free gingival graft, resulted in less vertical and horizontal changes of the alveolar ridge as compared with controls 6 months after extraction (Jung, Philipp et al. 2013).

2.0 AIMS

Aim 1: To evaluate the clinical and radiographic changes following socket graft + use of collagen dressing or 3D-collagen matrix between baseline and month-6.

Aim 2: To evaluate the volume changes on soft tissue following socket graft + use of collagen dressing or 3D-collagen matrix between baseline and month-6, and wound healing assessment.

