3.0 STUDY DESIGN

[figure not shown]
This study will be a randomized clinical trial involving a total of 24 subjects. We propose to recruit subjects into 2 groups: 1) Extraction treated with xenograft bone substitute (BioOss Collagen®) + collagen dressing (HeliPlug®), 2) Extraction treated with xenograft bone substitute (BioOss Collagen®) + 3D-collagen matrix (Mucograft Seal®). All subjects recruited will have already been approved and treatment planned for extraction + implant placement by non-study personnel to avoid any potential conflict of interest. All subjects will have radiographs that show the tooth planned for extraction. Each subject will be eligible for only 1 tooth extraction + dental implant rehabilitation. After tooth extraction, subjects will receive a standard site preservation therapy consisted with xenograft bone substitute + collagen dressing or the alternative site preservation therapy consisted with xenograft bone substitute + 3D-collagen matrix. After the conventional 6-month healing period, subjects will receive a dental implant in the previous extracted site. During the dental implant procedure, a 2x5mm bone core biopsy + a 2mm gingival biopsy will be obtained from the implant site.

Biopsy samples will be stored for future histological and histochemical analysis. After dental implant placement, all subjects will receive a healing abutment for soft tissue healing prior to implant restoration.

During the 6-month healing time after tooth extraction and site preservation therapy, subjects will return at week-1, week-2, week-4, month-3, and month-6 for intra-oral scanning for soft tissue volumetric acquirement. Subjects will receive a Cone beam computed tomography (CBCT) prior to extraction for the baseline hard-tissue volume measurement and appropriate extraction planning and at 6-month post-extraction for volumetric measurement and appropriate implant treatment planning.

Hard tissue analysis will be performed to compare linear ridge remodeling (baseline vs. 6-month healing). CBCT images will be analyzed by non-contact reverse engineering system (Geomagic software). Soft tissue volumetric analysis will be performed to compare the soft tissue healing between BioOss Collagen + Mucograft Seal and BioOss Collagen + Collagen Dressing. Images captured with an intra-oral scanner (Trios, 3Shape) collected at baseline, week-1, -2, -4, month-3, and month-6.

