Subjects in both groups will be instructed to rinse twice daily with 0.12% chlorhexidine gluconate for 30 seconds and avoid brushing or touching the area of extraction for 2 weeks. After 2 weeks, subjects may resume gentle brushing of the surgical site with a soft toothbrush. Sutures will be removed 2 weeks following the surgical appointment. Subjects will return at 1 week and 4 weeks to assess plaque control and wound healing.

Subjects will be given prescriptions for postoperative medications as stated in Table 1. Patient will assume all costs for prescription medications. Temporary appliance to replace the missing tooth will not be delivered as part of the study. However, subjects can have their referring dentists fabricating and delivering a temporary appliance to replace the missing tooth during the first 6 months of the study. The temporary appliance will not be covered by the study.

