5.4 VISIT 3 (DAY 7 +/- 2 DAYS)

Visit 3 may occur within 7 days of visit 2 (+/-2 days). The following procedures will be performed:

- Study personnel will record changes in medical history and concomitant medications since the previous visit and ask continuance criteria questions.
- Participant vital signs (blood pressure and pulse) will be recorded.
- Two (2) gingival crevicular fluid (GCF) samples will be collected from the surgical site for archiving and later regenerative and inflammatory biomarker analysis. The GCF will be collected from the interproximal site of the surgical site without disturbing the healing.
- 3Shape Trios scanning will be completed for later volumetric analysis.
- The participant will be re-instructed to defer oral hygiene measures in the surgical site.
- Adverse events will be monitored and recorded as necessary

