5.5 VISIT 4 (DAY 14 +/- 2 DAYS)

Visit 4 may occur within 7 days of visit 3 (+/-2 days). The following procedures will be performed:

- Study personnel will record changes in medical history and concomitant medications since the previous visit and ask continuance criteria questions.
- Participant vital signs (blood pressure and pulse) will be recorded.
- Two (2) GCF samples will be collected from the surgical site for archiving and later regenerative and inflammatory biomarker analysis. The GCF will be collected from the interproximal site of the surgical site without disturbing the healing.
- 3Shape Trios scanning will be completed for later volumetric analysis.
- Sutures will be removed if still present.
- The participant will be instructed to resume oral hygiene measures in the surgical site.
- Adverse events will be monitored and recorded as necessary

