5.6 VISIT 5 (DAY 28 +/- 2 DAYS)

Visit 5 may occur within 14 days of visit 4 (+/-2 days). The following procedures will be performed:

- Study personnel will record changes in medical history and concomitant medications since the previous visit and ask continuance criteria questions.
- Participant vital signs (blood pressure and pulse) will be recorded.

- Two (2) GCF samples will be collected from the surgical site for archiving and later regenerative and inflammatory biomarker analysis. The GCF will be collected from the interproximal site of the surgical site without disturbing the healing.
- 3Shape Trios scanning will be completed for later volumetric analysis.
- The participant will be instructed to continue oral hygiene measures in the surgical site.
- Adverse events will be monitored and recorded as necessary

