7.0 STATISTICAL ANALYSIS

Descriptive statistics (means and standard deviations for continuous variables and frequencies for categorical variables) will be produced for vital signs, demographic characteristics, medical history and clinical variables, both overall, and for each of the two groups of study participants. Summaries of clinical variables will be presented at baseline and at study exit. Adverse events (including onset, duration, treatment, outcome and suspected causality) and reasons for withdrawals will be listed and summarized.

A power analysis was performed using a statistical power calculator (SAS Power Procedure, Cary, NC). This study will have a sample size of 24 subjects, 12 in each of the two groups. We will have at least 90% power (with a Type I error rate of 5%) to detect a difference of 2.5mm in the horizontal ridge width measured at 3mm below the most coronal aspect of the crest, assuming a standard deviation of 1.6mm, as determined by a previous study (Jung, Philipp et al. 2013). This power calculation takes into account the estimated 10% of subjects drop out. A “p” value of less than 0.05 will be considered statistically significant.

For soft tissue analysis, the primary outcome was the within-participant difference between the linear and volume changes at the test and control groups. These differences were measured in each participant prior to surgery, as well as 3 and 6 months after surgery, leading to a series of three longitudinal differences for each participant. For each group, the differences at all three time points were analyzed simultaneously using a linear mixed model (LMM), in which the actual linear and volume measures were modeled as a function of time (categorical), treatment group, and the interaction of time and treatment, while accounting for the repeated measures on each participant with a random participant effect. Given that both time and treatment are categorical, our approach was a generalized version of repeated measures ANOVA, as our LMM allowed for differing variability in linear and volume measures at each time point. Within each LMM, we also tested for a difference between the two treatment groups with respect to the overall time pattern in linear and volume measures. Due to the exploratory nature of the analysis, no Bonferroni correction for multiple testing was applied. Statistical significance was defined as a p -value < 0.05 .

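### Aim 2 includes wound healing, but no visit list, outcome definition or analysis carries it through, and the section 7.0 model omits the week-1, week-2 and week-4 scans that section 6.6 plans to compare

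*Combined protocol and SAP*

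**What the plan says.** **Aim and timing.** Section 2.0 gives Aim 2 two parts: soft-tissue volume change from baseline to month 6, "and wound healing assessment". Section 5.3 (Visit 2, Day 0) says when the second part happens: "Subjects will return at 1 week and 4 weeks to assess plaque control and wound healing".

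**Visit lists.** Sections 5.4, 5.5 and 5.6 (days 7, 14 and 28) list medical history, vital signs, crevicular fluid samples, an intra-oral scan, hygiene instruction and adverse events. Day 14 adds suture removal. The entries closest to the wound are "The participant will be re-instructed to defer oral hygiene measures in the surgical site" (day 7), "Sutures will be removed if still present" (day 14) and "The participant will be instructed to continue oral hygiene measures in the surgical site" (day 28).

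**Scans.** Section 3.0 states that "subjects will return at week-1, week-2, week-4, month-3, and month-6 for intra-oral scanning for soft tissue volumetric acquirement". Section 6.6 adds baseline, describes the purpose as comparing soft-tissue healing between the groups, and computes volume change at all six times.

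**Analysis.** Section 7.0 fits a linear mixed model to soft-tissue measurements taken "prior to surgery, as well as 3 and 6 months after surgery", that is, three times per participant.

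**Background.** Section 1.4.3 cites a trial of the same matrix against spontaneous healing. Open-defect area was smaller with the matrix at days 4 and 8, and "re-epithelization was completed in all subjects by day 15". Section 1.4.2 cites a study of sockets covered with connective-tissue grafts in which all sockets had closed 4 weeks after extraction.

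**The concern.** A stated aim should lead to a measurement, a time and a comparison. Here wound healing has a time (weeks 1 and 4) but no measurement and no comparison. The soft-tissue scans from the same weeks are to be collected and, under section 6.6, measured, yet the only inferential model leaves them out.

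Two things are at stake. First, if section 7.0 is followed, the healing part of Aim 2 produces no between-arm result, and the early scans can at most be described. Second, if the gap is noticed later, the measure and the week would be chosen after the data are available. Section 7.0 tests at 0.05 with no multiplicity correction, so a healing result chosen in that way would be hard to interpret.

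**Working it through.** **Step 1. Follow wound healing through the document.**

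| Place | What it contains on wound healing |
|---|---|
| 2.0, Aim 2 | Named as part of the aim |
| 5.3, Visit 2 | Assigned to the week-1 and week-4 returns; no scale named |
| 5.4, 5.5, 5.6 (Visits 3 to 5) | No item |
| 6.1 to 6.6 | Gingival index, probing depth, bleeding, attachment level, CBCT and soft-tissue volume are defined; no healing score, open area or time to closure |
| 7.0 | No healing analysis |
| 8.3 | General oral survey at each visit, scored normal or abnormal; no healing scale |

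**Step 2. Compare the soft-tissue time points.**

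- Sections 3.0 and 6.6: baseline, weeks 1, 2 and 4, months 3 and 6, so 6 times, 5 of them after extraction.
- Section 7.0: before surgery, months 3 and 6, so 3 times, 2 of them after extraction.
- Left out of the model: 5 − 2 = 3 scans per participant (3/5 = 60% of post-extraction scans to month 6). In 24 completers that is 3 × 24 = 72 scans.

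**Step 3. Compare the modelled times with the cited closure times.** The month-3 visit has a window of 7 days either way. Taking a month as 30 days, the earliest month-3 scan is on day 90 − 7 = 83. That is 83 − 15 = 68 days after the day-15 closure cited for mucosal wounds, and 83 − 28 = 55 days after the 4-week closure cited for graft-covered sockets.

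**Step 4. Check the plan's own power figure.** Inputs from section 7.0: difference 2.5 mm in ridge width, SD 1.6 mm, two-sided 5%, 12 per arm, 10% dropout. The standardised difference is 2.5/1.6 = 1.5625, and with n per arm the noncentrality is 1.5625 × √(n/2).

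- n = 12: noncentrality 3.83, power 95.5%.
- n = 11: power 93.6%. With 11 and 10: 92.4%.
- n = 10: noncentrality 3.49, power 91.0%.

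The claim of at least 90% reproduces. It concerns ridge width only, so this point does not touch it.

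**Step 5. What precision could an early comparison have?** For a single-visit comparison of two means, the 95% interval has half-width t × SD × √(2/n).

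- n = 12 (22 df): 2.074 × √(2/12) = 0.85 SD.
- n = 10 (18 df): 2.101 × √(2/10) = 0.94 SD.

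**Step 6. Illustration only, from the day-8 result in section 1.4.3.** The means were 11.7 (SD 2.5) and 13.6 (SD 2.9) mm².

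- Difference: 13.6 − 11.7 = 1.9 mm².
- Pooled SD: √((2.5² + 2.9²)/2) = √7.33 = 2.71 mm².
- Standardised difference: 1.9/2.71 = 0.70.
- Power for two independent arms: about 38% at 12 per arm and 32% at 10 per arm. About 33 per arm would be needed for 80%.

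That trial used a different wound type and comparator, so these are not planning figures. Together with Step 5 they show only that an early comparison here is an estimate, not a powered test.

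**The case against.** The strongest reply is that the plan does cover early healing. Section 5.3 schedules the assessment, section 8.3 adds an intraoral examination at every visit with abnormal findings described, and sections 3.0 and 6.6 present the volumetric analysis as the comparison of soft-tissue healing, with weeks 1, 2 and 4 included. On that view only the list of times in section 7.0 is wrong.

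Much of this stands. A reader might infer that no visit assesses healing, or that the plan ignores the early weeks. The documents support neither: section 5.3 names the visits and section 6.6 plans volume measurement at those weeks. The time-point problem is a conflict between sections 6.6 and 7.0, not an absence of any plan. It does not remove the gap, though. Aim 2 lists healing in addition to volume, so volume does not obviously serve for both. Even if it does, the model in section 7.0 excludes the early volumes. The examination in section 8.3 is a general normal/abnormal survey, not an outcome.

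A second reply is that late times are a legitimate target. That also stands. A reader might infer that the matrix can act only in the first two weeks, so that months 3 and 6 are uninformative. Section 1.4.3 also cites less ridge change at 6 months with the bone substitute plus this matrix than in controls, and the volume part of Aim 2 is explicitly set at month 6. What months 3 and 6 miss is a difference in wound closure.

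A third reply is that consequences are limited: the soft-tissue analysis is labelled exploratory and the sample size rests on ridge width. Both are true, and they limit the importance of the point without answering it.

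**Conclusion.** The point holds in two parts. Wound healing is named in Aim 2 and assigned to weeks 1 and 4, but has no defined measure, no visit-list item and no analysis. Separately, section 7.0 models three soft-tissue times where sections 3.0 and 6.6 plan six, so three of five post-extraction scans to month 6 (72 in 24 completers) enter no between-arm test. As written, the early healing period has no between-arm analysis although the scans are collected.

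The statement that months 3 and 6 cannot show a closure difference assumes that closure here takes roughly as long as in the cited studies. Neither matches this trial: one studied oral mucosal wounds (by its title in the reference list), the other sockets under soft-tissue grafts. Closure would have to take about 12 weeks or more for the statement to fail.

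A reader might take 0.70 SD as the size of effect being missed. The documents do not support that, because the comparator was spontaneous healing rather than a collagen dressing over grafted bone.

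This should be corrected, but it does not threaten the hard-tissue comparison or the sample size.

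**What to change.** 1. Amend section 7.0 so that the soft-tissue mixed model uses all six scan times in section 6.6. Report the week-1, week-2 and week-4 treatment contrasts as secondary estimates with 95% confidence intervals, alongside the month-3 and month-6 contrasts.
2. Pre-specify one wound-healing measure for the existing week-1 and week-4 visits. Add it to sections 5.4 and 5.6, define it in section 6, and state in section 7.0 how the arms are compared and which visit is the main one. Week 4 coincides with the later cited closure time, so little difference may remain by then.
3. Use open-wound area from the scans only if the sponsor confirms that they can show it. Section 6.6 describes surface superimposition and volume subtraction, and nothing in the documents says that uncovered tissue can be distinguished. Otherwise use a defined clinical score at the same visits.
4. Say who assesses healing and whether they are masked. Section 3.1 masks volumetric assessments only. Under section 5.3 the test arm has non-resorbable and resorbable sutures and the control arm resorbable only, so images taken before suture removal may reveal the arm. The plan should state this limitation.

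**Cost.** No new visit and no change to the sample size. There is some extra measurement, one item on two visit forms and a short amendment. The model estimates six time-specific variances instead of three from 24 participants, and the overall time-by-treatment test goes from (3 − 1) × (2 − 1) = 2 to (6 − 1) × (2 − 1) = 5 degrees of freedom. Early contrasts will be imprecise: for a single-visit comparison, about ±0.85 SD at 12 per arm.
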